4.1 Recruitment, Eligibility Criteria, and Screening

From May 2021 to December 2023, research assistants recruited participants through primary care clinics and community organizations (e.g., food banks) in urban and rural locations throughout the province of Alberta, Canada.

Adults aged 18-85 years with T2DM were eligible to participate if they: 1) had persistent hyperglycemia, defined as an A1C between 6.5-12% at baseline (0 months); blood glucose levels below 6.5% are considered clinically acceptable and those above 12% require urgent anti-hyperglycemic treatment with insulin, 2) experienced household food insecurity in the past 6 months, indicated by answering affirmatively to at least one question on Health Canada's Household Food Security Survey Module (HFSSM)⁴³, 3) spoke English or had someone to assist them during the study, and 4) were willing to travel to Calgary or Edmonton to complete data collection if they were not referred by a primary care clinician

Exclusion criteria included significant diabetes complications (i.e., intensive insulin therapy, current metabolic decompensation, diabetic ketoacidosis and/or hyperglycemic hyperosmolar emergency within the past year, recurrent severe hypoglycemia within the past 3 months, hypoglycemic unawareness), and conditions that may have influenced typical dietary patterns (i.e., pregnancy, breastfeeding, diagnosed eating disorder). Participants were excluded if they resided in a facility that provided meals (e.g., retirement home), were participating in other clinical trials that might interfere with the FoodRx program, did not have ongoing and reasonable access to

study-affiliated supermarkets, planned to leave Canada for more than 2 weeks at a time during the intervention, and/or had other household members that participated in the study.

Researchers assessed eligibility at baseline (0 months) using a screening questionnaire and participants indicated their informed consent to participate prior to beginning baseline data collection.

4.2 Sample Size

The sample size calculation was based on A1C, the primary outcome for the RCT. A mean baseline A1C of 8.5% (SD=1.4%) was expected in our population based on local administrative data.⁴⁴ For 90% power to detect a minimally important clinical difference in A1C of 0.5%⁴⁵, 594 participants were required assuming 5% type 1 error, 30% attrition⁴⁶, and potential design effects based on sampling in different primary care clinics and communities (25% inflation).

4.3 Stopping Guidance and Interim Analysis

The FoodRx program was deemed a low risk to cause adverse events; thus, no stopping guidance was required, and no interim analyses were planned or conducted. Participants continued their regular care with their primary care physician and/or other care providers during the trial, including adjustments to medication regimes to improve glycemia at the providers discretion. At the conclusion of the study, participants continued to be followed by their care providers.

4.4 Analysis Timing and Data Cleaning

Analyses will commence in fall 2025, beginning with the primary outcome. Analyses for secondary and exploratory outcomes will commence in late fall of 2025. We will maintain an audit file documenting data cleaning and preparation processes.

4.5 Baseline Characteristics

At baseline, we collected data on blocking variables (i.e., gender identity, recruitment location, A1C), and sociodemographic and health-related characteristics including date of birth, sex at birth, race/ethnicity and Indigenous identity, Canadian citizenship², years lived in Canada, postal code*, home ownership, marital status, household size and composition, household changes*, relocation during the FoodRx program*, educational attainment, education location*, annual household income, main income source, participation in income support programs, access to extended health benefits, employment status, smoking status, duration of diabetes, and number of household members with T2DM with space to identify the member (e.g., daughter).

5. Outcomes

This section is comprised of outcome descriptions including definitions, variable types, measurement, scoring, and cut points as applicable for each outcome. Non-RCT outcomes included in Section 7 are also described herein. All statistical models are described in Section 7.

5.1 Primary Outcome

T2DM is a chronic metabolic disorder characterized by high blood glucose levels resulting from insulin resistance and/or impaired insulin secretion by the pancreas.⁴⁷ Monitoring blood glucose is essential to effective T2DM management. In this study, glycemic control was primarily quantified using A1C, which reflects average blood glucose levels over the previous 3 months.⁴⁸ An absolute reduction of 0.5% in A1C is achievable through improving diet quality^{8, 9} and is considered a clinically meaningful difference.⁴⁵ The 12-month FoodRx program provided adequate time to see dietary changes in 4 A1C cycles.

² *Indicates this characteristic was added after protocol registration.

The priority source for A1C will be blood samples, which participants provided at an Alberta Precision Laboratory or DynaLIFE Medical Lab of their choice. Blood sample collection and testing were standardized to the Diabetes Complications and Control Trial.⁴⁹⁻⁵² When A1C results are not available from blood samples participants' provided specifically for the RCT, we will extract A1C results from medical records and/or the Alberta Health Services' Analytics Data Integration, Measurement, and Reporting database. For extracted A1C, we will use results that were collected 3 months before or after the time point of interest (e.g., 3 months before or after the participant's post-intervention lab collection date). We will analyze 12-month A1C as a continuous outcome.

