The second element was a weekly healthy food incentive of CDN\$10.50 per household member for 12 months. Participants earned the weekly incentive by purchasing whole, minimally processed foods with little to no added fat, sugar, or salt from all food groups in study-affiliated supermarkets, which were part of a large chain with multiple banners and locations.^{8, 39} Incentive-eligible foods included dairy products; whole grain bread, pasta, and cereal; fresh, frozen, and canned vegetables; fresh and frozen fruit; fresh, plain meats, fish, and poultry; canned fish and meat alternatives (eggs, canned and dried beans, plain almonds). Researchers calculated incentive amounts based on total household size as reported at baseline (0 months), which was communicated to participants after randomization. Once participants reached their spending threshold as defined by their household size, they immediately received loyalty card points equal to their eligible spending (e.g., a two-person household spending CDN\$21 received CDN\$21 in points). The incentive was capped at CDN\$10.50 per person per week, and points were only given to households that met or exceeded their threshold each week. Although progress towards meeting the minimum spend was reset weekly, earned points carried over between weeks, did not expire, and could be redeemed for anything in-store in CDN\$10 increments. However, participants were encouraged to use these points to continue the earn-reward cycle by purchasing incentive-eligible foods. At baseline, participants' loyalty cards were preloaded with points equivalent to one week's incentive amount to allow initial participation without paying out-of-pocket. The incentive redemption mechanism was pilot tested⁴⁰ and is fully described elsewhere.³²

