3.3 Data Collection Schedule and Data Sources

Participants in both groups completed data collection at baseline (0-months), mid- (6-months), and post-intervention (12-months with data collection beginning 2 weeks prior to participants' program end date). Participants completed a self-administered online questionnaire in REDCap⁴¹, 2 online 24-hour dietary recalls using the Automated Self-Administered 24-Hour Dietary Assessment Tool for Canada (ASA24-2018-Canada)⁴², and biochemical and physical measurements (e.g., blood samples, height, weight, skin carotenoids) as per the schedule in Figure 1.

[figure not shown]

Figure 1: Data Collection Schedule

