5.2 Secondary Outcomes

5.2.1 Blood Glucose Levels

Glycemic control will also be assessed by 1) examining A1C levels as a continuous outcome at 6- and 18-months* to assess effectiveness of the intervention at midpoint and 6 months after cessation, 2) calculating the proportion of participants with elevated A1C as a binary outcome (A1C \geq 8.5%), and 3) examining fructosamine levels at 6- and 12-months as a continuous outcome as A1C can be unreliable for some participants⁵³⁻⁵⁵ and fructosamine is more sensitive to acute changes.⁵⁶

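### Does the 3-month window for extracted A1C need a named anchor and a cut-off at program end for the 12-month primary outcome?

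*SAP*

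**What the plan says.** Section 5.1 gives priority to blood samples provided for the trial. Records are used only as a fallback: "When A1C results are not available from blood samples". For extracted values the rule is "we will use results that were collected 3 months before or after the time point of interest", with the participant's "post-intervention lab collection date" as the example of a time point. The same section describes "A1C, which reflects average blood glucose levels over the previous 3 months".

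Section 3.2 pays the incentive "per household member for 12 months", and adds that "earned points carried over between weeks, did not expire, and could be redeemed for anything in-store". Section 3.3 places the last visit at "12-months with data collection beginning 2 weeks prior to" the program end date. Section 5.2.1 makes 6- and 18-month A1C secondary outcomes, "to assess effectiveness of the intervention at midpoint and 6 months after cessation".

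Section 6.3 commits to using all available data. In Section 7.4 the primary model contains a data-source indicator and the number of days since baseline. The sensitivity analyses for 12-month A1C include one without administrative values and one with a term for deviation from the 12-month collection point.

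**The concern.** Two features look wrong on first reading.

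- **Anchor.** Extraction is triggered by having no study A1C, yet the example anchor is the date of the study lab visit. Many of the people concerned will have no such date. The SAP names no other anchor and no rule for choosing among several eligible results. Two analysts could in principle build different primary datasets.
- **Late values.** The window closes 3 months after its anchor, but nothing stops it at program end. On the SAP's own 3-month look-back, a value drawn 3 months after program end describes only time without the incentive. Section 5.2.1 treats that period as a separate question.

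If the effect fades once the incentive stops, late values pull the primary contrast toward zero. That could matter for a borderline estimate, because Section 2.1 frames the hypotheses around a difference of at least 0.5%. The source and timing terms in Section 7.4 are listed as covariates, with no stated interaction with group. They shift both arms alike and do not restore a contrast that has faded.

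**Working it through.** **Inputs from the SAP.** SD 1.4, difference 0.5, 90% power, 5% type 1 error (taken as two-sided), 30% attrition, 25% design inflation, N = 594 (Section 4.2). Look-back W = 3 months = 91.25 days (Section 5.1). Collection opens 14 days before program end (Section 3.3).

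**Assumed, because the SAP does not give them.** Extracted share p of 12-month values: 10%, 20% or 30%. Equal weight over the look-back. Effect stops with the incentive, unless stated otherwise.

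**The plan's own figure.** 2 × 1.4² × (1.960 + 1.282)² / 0.5² = 164.8, so 165 per arm. 330 × 1.25 / 0.70 = 589; with 166 per arm (t-test) it is 593. This agrees with 594 to within rounding. Effective number: 594 × 0.70 / 1.25 = 332.6, or 166.3 per arm. SE = 1.4 × √(2/166.3) = 0.1535, and power for 0.5 is 90.3%.

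**Current rule.** A value drawn t days after program end has post-program share t/91.25.

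- Anchor at program end, draws spread evenly: mean share 0.25. Contrast = 0.5 × (1 − 0.25p) = 0.488, 0.475, 0.463.
- Same anchor, all extracted values after program end: mean share 0.5. Contrast = 0.475, 0.450, 0.425.
- Anchor 14 days earlier, even spread: mean share 0.5 × 77.25² / (91.25 × 182.5) = 0.179. Contrast = 0.491, 0.482, 0.473.
- Full persistence of the effect: 0.500 throughout.

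Even-spread bias is 0.0125 to 0.0375, that is 0.08 to 0.24 of the SE. In the all-late case it is 0.025 to 0.075, or 0.16 to 0.49 of the SE.

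**How much the choice of anchor matters.** At p = 30%, the two anchors differ by 0.5 × 0.3 × (0.25 − 0.179) = 0.011 (even). If all values are late, the earlier anchor has mean share 77.25 / (2 × 91.25) = 0.423, and the difference is 0.5 × 0.3 × (0.5 − 0.423) = 0.012. Both are under a tenth of the SE.

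**A late limit of g days after program end.**

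- Values lost, L: p(91.25 − g)/182.5 (even) or p(91.25 − g)/91.25 (all late).
- Mean post-program share s among extracted values kept: g²/(2W)/(g + W) (even) or g/(2W) (all late).
- Contrast = 0.5 × [1 − s(p − L)/(1 − L)]; SE = 0.1535/√(1 − L); RMSE = √(bias² + SE²).

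Example, p = 30%, even, g = 45: L = 0.3 × 46.25/182.5 = 0.076; s = 0.0814; contrast = 0.5 × (1 − 0.0814 × 0.224/0.924) = 0.490; SE = 0.1597; RMSE = 0.1600.

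| Extracted share, spread | RMSE, current | RMSE, 45-day | RMSE, 14-day | Lost, 45-day | Lost, 14-day |
|---|---|---|---|---|---|
| 10%, even | 0.1540 | 0.1555 | 0.1569 | 2.5% | 4.2% |
| 20%, even | 0.1555 | 0.1577 | 0.1605 | 5.1% | 8.5% |
| 30%, even | 0.1580 | 0.1600 | 0.1643 | 7.6% | 12.7% |
| 10%, all late | 0.1555 | 0.1577 | 0.1605 | 5.1% | 8.5% |
| 20%, all late | 0.1615 | 0.1625 | 0.1684 | 10.1% | 16.9% |
| 30%, all late | 0.1709 | 0.1681 | 0.1778 | 15.2% | 25.4% |

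The 45-day limit lowers RMSE only in the last row. The 14-day limit lowers it in none.

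**Power at p = 30%, even spread, current against 45-day limit.** 0.854 to 0.866 if the effect stops with the incentive; 0.903 to 0.879 if it persists fully. Information recovered from 6-month data is ignored throughout.

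**The case for a change.** The strongest case for a change is that naming the anchor, taking the closest result and using each result once would cost almost nothing and would remove discretion from the primary endpoint. The planned analyses do not isolate timing: dropping all administrative values also drops well-timed ones, and the analysis with a timing-deviation term largely repeats the primary model.

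That description is accurate, and a line naming the anchor would do no harm. But the lab date is only an example; the rule itself refers to the time point of interest. Section 3.3 ties the 12-month visit to program end, and Section 7.4 measures deviation from a 12-month point. An analyst facing a participant without a lab date would use that scheduled date and the nearest result. With nominal anchors, the windows for 6, 12 and 18 months (3–9, 9–15 and 15–21 months) meet only at their end points, so double use hardly arises. Section 3.4 keeps those who analyze the data blind to allocation, which limits selection by arm. A closing date for study samples cannot be called missing either: Section 3.3 refers to Figure 1, which is not reproduced in the text at hand, and to a separate protocol.

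The case for a late limit does better if covariate adjustment shrinks the SE. With an assumed 20% cut and p = 30%, RMSE (current, 45-day, 14-day) is 0.128, 0.128, 0.131 for even spread and 0.144, 0.135, 0.142 if all values are late. So the limit helps where many values are extracted and all are late. That corner is remote: with the planned 30% attrition, p = 30% means that only 0.7 × 0.7 = 49% of participants gave a 12-month study sample.

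**Conclusion.** No change follows. The anchor and the choice among several results are details that analysts would fill in sensibly from Sections 3.3 and 7.4, and the choice between plausible anchors moves the contrast by about 0.01.

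The open late side is a fair trade-off. The wide window recovers outcomes for participants without a study sample, in line with Section 6.3. The price is a possible bias toward zero of 0.0125 to 0.0375 under even spread, 0.075 in the worst case examined, and none if the effect persists, which unexpired points make possible. The bias cannot create a false positive result. A late limit would exchange it for lost data and heavier reliance on missing at random, usually with slightly larger total error. The planned analysis without administrative values already shows whether extracted results drive the finding.

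This rests on assumed extracted shares of 10% to 30%, equal weighting over the look-back and immediate fading. The SAP gives none of these. A much larger share of extracted values, drawn mostly late, would weaken the conclusion.

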5.2 Secondary Outcomes

5.2.1 Blood Glucose Levels

Glycemic control will also be assessed by 1) examining A1C levels as a continuous outcome at 6- and 18-months* to assess effectiveness of the intervention at midpoint and 6 months after cessation, 2) calculating the proportion of participants with elevated A1C as a binary outcome (A1C \geq 8.5%), and 3) examining fructosamine levels at 6- and 12-months as a continuous outcome as A1C can be unreliable for some participants⁵³⁻⁵⁵ and fructosamine is more sensitive to acute changes.⁵⁶

5.2.2 Clinical Health Markers

Biochemical/Physical Measurements The following biochemical and physical measurements for blood lipids, blood pressure, BMI, and waist circumference were collected for each participant. All measurements adhered to standardized measurement protocols and were performed a minimum of two times by trained researchers/clinicians.

1. Blood lipids include total cholesterol, high-density lipoprotein (HDL) cholesterol, low-density lipoprotein (LDL) cholesterol, triglycerides, and apolipoprotein B (Apo B). Dyslipidemia, defined as atypical blood lipid levels, is a common comorbidity in T2DM and can increase the risk of cardiovascular disease and other diabetes related complications. Blood lipids were measured by means of blood samples. Lipids will be analyzed as continuous outcomes.
2. Blood pressure is measured via systolic and diastolic blood pressure values. Hypertension, defined as persistent elevated blood pressure, is a common comorbidity in T2DM, and can increase the risk of numerous diabetes related complications. Systolic and diastolic blood pressure were measured with Automatic Professional Blood Pressure monitors from BIOS Medical from the approved Hypertension Canada list. Systolic and diastolic blood pressure will be analyzed as continuous outcomes.
3. BMI is an indicator of adiposity.⁵⁷ Excess body fat is associated with poor glycemic control, increased insulin resistance, and increased cardiometabolic risk. BMI will be calculated using height as measured with a stadiometer, and body weight as measured with a digital scale with no shoes and light clothing. BMI will be analyzed as a continuous outcome.
4. Waist circumference is a clinical measure of abdominal adiposity, which is strongly associated with insulin resistance, and increased risk of cardiovascular disease.⁵⁸ Waist circumference was measured with non-elastic Seca 201 measuring tapes at the mid-point between the lowest border of the rib cage and the iliac crest.⁵⁹ Waist circumference will be analyzed as a continuous outcome.

Need for Antihyperglycemic Medication/Insulin Diet quality has significant impacts on glycemic control in the management of T2DM, including the need for antihyperglycemic medications and insulin use. Evidence indicates as diet quality improves, the need for medications/insulin can be de-intensified or discontinued altogether.⁶⁰ Data to assess this outcome will be extracted from the Pharmaceutical Information Network (PIN) database.⁶¹ Need for antihyperglycemic medication/insulin will be quantified by monitoring changes in medication/insulin 1) usage, defined as initiation or discontinuation, and 2) type including Metformin, Sulfonylureas, Repaglinide, DPP-4 inhibitors, GLP1 receptor agonists, SGLT2-inhibitors, Acarbose, Thiazolidinediones. Need for antihyperglycemic medication/insulin will be analyzed as an ordinal outcome.

We will use a novel scoring system that assigns points for each change based on its anticipated impact on A1C. Points will be attributed cumulatively for all qualifying changes during the program.

For an expected change in A1C of ~0.5%, 1 point will be assigned to the following changes.

- less than full dose of Metformin (<2000 mg/day) or Sulfonylureas (Gliclazide<60 mg/day, Glyburide <10 mg/day) or Repaglinide (<5 mg/day)
- any dose of DPP-4 inhibitor, SGLT2-inhibitor or Acarbose
- initiation of basal insulin

For an expected change in A1C of ~1%, 2 points will be assigned to the following changes.

- full dose of Metformin, Sulfonylureas or Repaglinide
- any dose of GLP1 receptor agonists or Thiazolidinedione
- initiation of bolus insulin

Addition of medication/insulin will be scored positively and reductions scored negatively to arrive at a final cumulative medication/insulin adjustment score for each participant. Deintensification will be considered a positive, and intensification will be considered a negative.

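### For metformin, sulfonylureas and repaglinide, the medication/insulin score does not say how a move between dose tiers is scored; read literally, the same start and end regimen can score +2 or +3

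*SAP*

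**What the plan says.** Section 5.2.2 builds the secondary outcome on need for antihyperglycemic medication/insulin from pharmacy dispensing data (the PIN database). The parts that matter here are:

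- What counts as a change: "usage, defined as initiation or discontinuation, and 2) type including Metformin" and the other listed classes. Dose is not named in this definition.
- The unit scored: "We will use a novel scoring system that assigns points for each change based on its anticipated impact on A1C".
- The calibration: "For an expected change in A1C of ~0.5%, 1 point will be assigned to the following changes". Two points go with an expected change of about 1%.
- The lower tier, 1 point: "less than full dose of Metformin (<2000 mg/day) or Sulfonylureas (Gliclazide<60 mg/day, Glyburide <10 mg/day) or Repaglinide (<5 mg/day").
- The upper tier, 2 points: "full dose of Metformin, Sulfonylureas or Repaglinide".
- Accumulation: "Points will be attributed cumulatively for all qualifying changes during the program".
- The sign rule: "Addition of medication/insulin will be scored positively and reductions scored negatively to arrive at a final cumulative medication/insulin adjustment score for each participant".

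The remaining oral and injectable classes carry one fixed value at any dose: 1 point for DPP-4 inhibitors, SGLT2 inhibitors and acarbose, and 2 points for GLP1 receptor agonists and thiazolidinediones. Insulin appears only as initiation, with 1 point for basal and 2 for bolus.

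Section 7.4 analyses the outcome as ordinal and adjusts for its baseline value. Section 4.3 leaves treatment to the care providers, "including adjustments to medication regimes to improve glycemia at the providers discretion".

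**The concern.** The points are attached to states but awarded per change. For a class with two tiers these are different things. A participant who passes through the lower tier on the way to the upper one can collect both sets of points, although the expected A1C effect of the final state is the upper tier's alone. The score would then depend on the route taken as well as on where treatment began and ended.

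Because providers adjust treatment freely, the outcome is meant to show whether net need for medication differs between arms. If titration steps add points of their own, part of the score measures how gradually a provider titrates. Even if the text is regarded as merely silent, two analysts could derive different values from the same dispensing records.

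**Working it through.** The SAP gives no figure to reproduce; the check applies its rule to example courses. All point values are those of Section 5.2.2. For one tiered class, let the states be none (0 points), below full dose (1 point) and full dose (2 points).

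Three ways of scoring a step are compared:

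- **L1, literal:** a step up earns the points of the tier reached; a step down to below full dose scores -1; a stop scores minus the points of the tier left.
- **L2, literal:** steps up as in L1; any reduction scores minus the points of the tier left.
- **D, difference:** each step scores the points of the new state minus those of the old one.

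Two literal versions are needed because the SAP does not say how a step down between tiers is scored.

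| Course | L1 | L2 | D |
|---|---|---|---|
| none, full | 2 | 2 | 2 |
| none, below full, full | 1 + 2 = 3 | 3 | 1 + 1 = 2 |
| none, below full, full, none | 1 + 2 - 2 = 1 | 1 | 1 + 1 - 2 = 0 |
| none, below full, none | 1 - 1 = 0 | 0 | 0 |
| full, below full, full | -1 + 2 = 1 | -2 + 2 = 0 | -1 + 1 = 0 |

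**Same start, same end.** Rows 1 and 2 end in the same tier from the same start, yet score 2 and 3 under either literal version. The excess is (3 - 2) / 2 = 50%. At about 0.5% A1C per point, the implied effect is 3 x 0.5 = 1.5% against 2 x 0.5 = 1.0%, whereas the SAP attaches about 1% to full dose.

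**Return to baseline.** Row 3 applies the sign rule and still leaves +1.

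**All courses of up to four changes.** From none to full, the possible totals are 2, 3 or 4 under L1 and 1, 2 or 3 under L2. From none back to none they are 0 or 1 under L1 and -1, 0 or 1 under L2. Under D every start and end pair has exactly one value, and any return to baseline is 0.

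**Classes with one value at any dose.** Start then stop gives +1 - 1 = 0 or +2 - 2 = 0. The total depends only on start and end.

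**Insulin.** Start then stop gives 0 if the stop is scored negatively, as the sign rule implies. A dose change in someone already on insulin scores 0 on any reading.

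**Baseline value.** Section 7.4 adjusts for baseline need. A score accumulated from changes during the program has no value at program start, so that covariate is not defined by Section 5.2.2.

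**The case against.** The strongest reply is that the SAP never says a move from the lower to the upper tier earns 2 further points. Points follow the anticipated A1C impact of each change, and going from a state worth about 0.5% to one worth about 1% is itself a change of about 0.5%, hence 1 point. That is reading D, and under it the problem disappears. The argument is fair, and it is probably what was intended. But no sentence states it, and awarding listed values per change and accumulating them points the other way.

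A second reply is that usage change means starting or stopping, so a dose step may not qualify at all. That does not rescue the rule. If only the start counts, starting below full dose and moving to full scores +1 against +2 for a direct start, so the route still matters. It also leaves the dose-dependent points at odds with a definition that omits dose.

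Two broader inferences should be resisted. A reader might infer that every class is path-dependent, or that plain starts and stops fail to cancel. The sign rule and the fixed values rule this out for the five classes scored at any dose. A reader might also infer that leaving out insulin dose is a scoring error. It follows the stated definition, and Section 7.4 plans an analysis of this outcome without participants taking insulin. It is a limitation to acknowledge.

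It also stands that Section 6.5 treats secondary outcomes as supportive and hypothesis-generating, and that participants with different baseline regimens should score differently on a change score.

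**Conclusion.** The point holds for metformin, sulfonylureas and repaglinide. Scoring of moves between tiers is unspecified, and the literal wording makes the score depend on the route: +3 instead of +2 for stepwise titration to full dose, and +1 instead of 0 after a later stop. Each surplus point conflicts with the SAP's own calibration by about 0.5% A1C.

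These are sizes for a single participant under the literal readings. It may be tempting to set that 0.5% beside the trial's 0.5% between-group difference, or to conclude that the arm comparison is biased. The documents support neither: they do not give the frequency of stepwise titration or say whether it differs by arm, and one participant's score is not comparable with a difference in means. The primary A1C test does not use this score and is unaffected.

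Two related gaps are independent of the reading chosen. The model's baseline covariate is undefined. The direction of the final score is also unclear, because additions carry positive points while de-intensification is to be regarded as favourable. The rule should be settled before the outcome is derived.

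**What to change.** Keep the existing point values and score the regimen:

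1. From PIN, compute one regimen score at program start and one at 12 months. Each class counts once at its current tier; basal and bolus insulin count when present. Analyse the 12-month score minus the start score. Equivalently, state that a change between tiers scores only the difference in points and that stopping removes the points held; the steps then sum to the same result. Remove the instruction to accumulate all qualifying changes, or qualify it in this way.
2. Name the start score as the baseline-need covariate in Section 7.4.
3. State which direction of the final score is favourable.
4. Reconcile the usage and type definition with the dose-dependent points.
5. Acknowledge that insulin dose changes are not scored. A separate report of insulin dose change among participants on insulin at baseline is optional, where PIN allows it.

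The cost is a few sentences and one derivation from data already planned. No dose threshold, point value or clinical rule changes. The downside is that changes reversed before 12 months no longer count; they can be listed descriptively.
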